3.4 Withdrawal and discontinuation

Participation in the study is voluntary and participants can withdraw from the study without any impairment of the quality of care. Potential reasons for not completing the study process or withdrawing from the study might be that women will withdraw from the study consent or not complete the antenatal education class. We estimate not completing the class will be rare. The loss of follow-up was considered in the sample calculation. Sociodemographic and pregnancy-related characteristics, which were collected before these participants dropped out from the study, will be compared with those completing the whole study. This will provide information, if systematic patterns of dropping outs can be observed and inform the generalisability of the results. The comparison might also give information, if inclusion and exclusion criteria should be re-evaluated in follow-up studies.

Data will be entered into REDCap®. The data base in REDCap® will be programmed at ZHAW and will enable data entry in the Canton Hospital Winterthur and data download by the sponsor-investigator at ZHAW to download it in different formats. Data will then be stored on a secured pool at ZHAW. Data is stored on a dedicated, encrypted project file share provided by ZHAW's IT department. Access is limited to project members (restricted access by IT) and requires ZHAW-managed user accounts. Password policies are enforced, logins are monitored and logged. File access is logged and auditing enabled. External access requires two-factor authentication (SMS token). Data is physically stored on centralized storage, with data redundancy across ZHAW's two data-centres, daily full backups and anti-ransomware measures in place. A centralized anti-malware solution continuously scans files for malicious content. Storage capacity is up to 500 GB. Individual files/folders can be restored by users from hourly (up to 2 days), daily (up to 9 days) and weekly snapshots (up to two months).

The participant identification list, which links the study numbers to personal details of women will be stored in a separate secured pool. If participants will withdraw from the study, their study key will be destroyed deleting all personal information from the study list and their anonymised data will be used for analyses that are possible with it.

4 STATISTICS AND METHODOLOGY

4.1 Statistical analysis plan and sample size calculation

The socio-demographic and obstetric characteristics will be described employing descriptive statistics including frequency and percentage, mean and standard deviation, median and percentiles. The primary outcomes and secondary maternal and neonatal variables like women's satisfaction with their childbirth experience, self-confidence, pain management, mobility during labour, duration of labour, bonding, 5-minute Apgar-Score and umbilical cord pH will be compared between the study groups using repeated-measures ANOVAs and generalized estimating equations and mixed effects models. Quantitative data is analysed using R. The significance level will be two-sided $\alpha = 0.05$.

The sample size in the intervention phase was calculated based on the scores for the variable of childbirth self-efficacy using G-Power software. Based on the randomised controlled trial of a self-efficacy enhancing educational programme (SEEEP) by Ip et al., (2009). This study reported an effect size of 0.78 in increasing self-efficacy in labour and an attrition rate of around 30.7%. In the proposed study, we therefore assume an overall moderate effect size of 0.75. Setting a power at 80%, a significance level of $p < .05$, a sample size of 29 per arm is needed for a two-arm repeated measures design (GPower, version 3.1). Assuming an attrition rate of 20%, the final sample size will be 35 in each arm and 70 participants in total.

The qualitative data collected from the attendant birth midwives will be conducted by a semi-structured interview guide. The data will be transcribed verbatim and analysed using content analysis (Kuckartz & Rädiker, 2022). The total target sample size for the individual interviews with midwives is 12-15. Variation enriches the results and can be achieved with 12 to 15 interviews. This is important to provide a good basis for the evaluation of the antenatal education class and the feasibility as well as the practicability of the skilled breathing and relaxation technique. Qualitative data will be analysed using MAXQDA. Any deviation from the original statistical plan will be described and justified in the final trial report.

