3.3 Study procedures

The study duration will be one and a half year. The recruitment period will be one year. Participants will be recruited in their second or beginning of third trimester of pregnancy. After

signing the consent form, participants will register for an antenatal education class. Due to the course organisation at the Cantonal Hospital Winterthur, randomisation is conducted at the course level. The randomisation is performed by envelopes with the corresponding information about the course (intervention yes or no). In the randomisation process the sponsor-investigator and local project leader will be excluded.

Prior to the start of the classes, the participants fill in the online baseline questionnaire, which was sent to them by email. After the antenatal class, at around 36 weeks of gestation, the participants complete the education online questionnaire. The study assistant transfers the birth data anonymously directly from the clinic system to REDCap®. Finally, the postpartum online questionnaire is completed within four weeks after the birth (see Figure 1).

[figure not shown]

Figure 5 Study process

The following table provides an overview on the study instruments and the timing of their application for data collection:

Table 1 Study instruments and timing of application

Questionnaires / Interview	Time of application	Content	Filled in by
Baseline questionnaire (T0)	After recruitment before the antenatal education class started	Socio-demographic data, medical and obstetric history, German versions of the Childbirth-Self-Efficacy Inventory	Participant
Education questionnaire (T1)	After intervention (around 36 weeks of gestation)	Data about the antenatal education class, German versions of the Childbirth-Self-Efficacy Inventory	Participant
Labour and birth questionnaire (T2)	After birth	Labour and birth outcomes for mother and child, early postpartum period	Research assistant
Postnatal questionnaire (T3)	Early postnatal questionnaire (within 4 weeks after birth)	German version of the Childbirth experience questionnaire, postnatal quality of life, Data about the antenatal education class	Participant
Semi-structured interview guide	After birth (within 10 working days)	Women's experience during birth, feasibility of the breathing and relaxation technique learned, self-efficacy and self-confidence observed	Research assistant and birth attendant midwives

3.3.1 Potential bias and measures, to reduce them:

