4.2 Handling of missing data and drop-outs

The data will be planned and analysed using the intent-to-treat principle (ITT). If missing data is >5%, the possibility of multiple imputation will be examined. We intend to minimise missing data and will for example design mandatory questions in the questionnaires and send reminders to participants to complete the follow-up questionnaires.

The dropout rate is estimated at about 10 % and was taken into account accordingly in the sample size calculation. Recruitment has to take place during pregnancy in order to be able to observe the evaluation of the intervention. In obstetrics, it is never possible to predict how the birth will proceed and how the childbirth experience will affect the participants. Therefore, loss of follow-up for medical reasons cannot be avoided. The research assistants as well as the lead midwife will monitor the study process on site and remind the participants to fill in the questionnaires.

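### Section 4.1 names no primary model, tested term or time point for self-efficacy; if the two-time group-by-time test decides, it is a valid change-score test, usually less precise than T1 adjusted for T0

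*Combined protocol and SAP*

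**What the plan says.** Section 4.1 deals with every quantitative outcome in one sentence, which ends "umbilical cord pH will be compared between the study groups using repeated-measures ANOVAs and generalized estimating equations and mixed effects models". It does not say which of the three methods decides the primary question, which term is tested (group, time or group-by-time), or at which time point.

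The baseline score is collected. In the instrument table of section 3.3, CBSEI is in the T0 questionnaire and again at T1, around 36 weeks ("Data about the antenatal education class, German versions of the Childbirth-Self-Efficacy Inventory"). It is not listed at T3. Sections 2.2 and 2.3 instead speak of self-efficacy, or both questionnaires, before and after birth, so these places need reconciling. Section 2.3 calls the design pre-post, which implies T0 as a repeated outcome. Section 2.2 lists potential covariates without baseline CBSEI, and section 3.3.1 adds multivariable regression without naming covariates.

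On sample size, section 4.1 says "a sample size of 29 per arm is needed for a two-arm repeated measures design", with an assumed effect of 0.75. It gives neither a within-woman correlation nor the SD to which 0.75 refers. On missing data, section 4.2 states intention to treat and adds: "If missing data is >5%, the possibility of multiple imputation will be examined". Section 3.3 says that "randomisation is conducted at the course level".

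**The concern.** With three methods listed and none designated, the reported result could be chosen after the data are seen. The promise in section 4.1 to justify deviations has little force against a plan that permits several analyses.

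The open choice also affects power. With two time points, the ANOVA interaction discards part of the information in the baseline score. Listing GEE and mixed models does not settle this, because an unconstrained group-by-time term in either gives the same change contrast when data are complete. In a trial of 70 women, the choice between change and baseline adjustment can matter as much as several extra women per arm.

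It also stays open whether women without a T1 score enter the primary comparison. A standard repeated-measures ANOVA drops them, while a mixed model can keep them.

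**Working it through.** **Inputs.** From section 4.1: two-sided alpha 0.05, effect 0.75, 80% power, 29 per arm, 35 per arm recruited, 20% attrition. From section 4.2: dropout of about 10%. From section 3.3: CBSEI at T0 and T1, course-level randomisation. Not in the documents, so assumed: r = 0.3/0.5/0.7, equal SDs at T0 and T1, the course ICC, and 4 courses of 7 women per arm.

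**1. The plan's own figure.** For a two-sample t-test at one time, the noncentrality is 0.75 × √(29/2) = 2.86 with 56 df. Power is 80.1% at 29 per arm and 78.7% at 28. So 29 reproduces as a single-time t-test that uses no baseline information, although the plan calls it a repeated measures design.

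**2. What the unnamed term tests.** With two times, the group-by-time F is the square of the change-score t (1.7949 for both on a simulated data set). If the group main effect decided instead, the pre-treatment score would halve the effect to 0.375, with variance (1+r)/2. Power at 29 per arm would then be 41/37/33%.

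**3. Variances on the T1 SD, no clustering.**
- Change: 2(1−r) × 2/n.
- T1 adjusted for T0: (1−r²) × 2/n in large samples.
- Ratio: 2/(1+r) = 1.54/1.33/1.18.
- Small-sample price of adjustment at n = 29: a factor of about 1 + 1/(2n−4) = 1 + 1/54 = 1.0185. Break-even is r = 2/1.0185 − 1 = 0.96.

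**4. Power with 0.75 on the T1 SD.** Example at n = 29, r = 0.3: the change SE is √(1.4 × 2/29) = 0.311, so 0.75/0.311 = 2.41 and power is 66%. The adjusted SE is √(0.91 × 2/29) = 0.251 before allowing for chance baseline imbalance, and power is 83% after it. Noncentral t gives, for r = 0.3/0.5/0.7:

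| Per arm | Meaning | Change | Adjusted |
|---|---|---|---|
| 28 | 35 × 0.8, all loss by T1 | 64/79/94% | 82/88/97% |
| 29 | plan's evaluable n | 66/80/95% | 83/89/97% |
| 35 | no loss by T1 | 74/87/98% | 90/94/99% |

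For 80% power the change test needs 41/29/18 per arm and the adjusted test 27/23/16.

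**5. Power with 0.75 on the change-score SD.** At 29 per arm the change test has 80.1% at every r, and the adjusted test about 93/89/85%.

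**6. Course-level randomisation.** Simulation with 4 courses of 7 per arm, course-mean t-test on 6 df, T0 slope estimated within course, 0.75 on the T1 SD; change against adjusted:

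| ICC | Course effect at T1 only | Same course effect at T0 and T1 |
|---|---|---|
| 0.05 | 44/54/69% v 56/62/73% | 53/67/87% v 62/73/89% |
| 0.10 | 38/47/57% v 48/53/60% | 56/70/89% v 58/71/88% |
| 0.15 | not tabulated | 58/72/90% v 54/69/88% |

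In the last column r is the within-course correlation. The reversal follows from the course-mean variances for courses of size m. Change cancels a stable course effect and leaves 2(1−r)(1−ICC)/m. Adjustment leaves (1−r)² × ICC + (1−r²)(1−ICC)/m. Change is smaller when ICC > 1/(1+m) = 1/8 = 0.125, at any r.

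**7. Missing T1 scores.** A complete-pairs ANOVA would omit 0.10 × 70 = 7 to 0.20 × 70 = 14 women, but only if all the loss in sections 4.1 and 4.2 occurs by T1.

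**The case against.** The strongest reply is that the change test is valid and unbiased under randomisation, so preferring adjustment is an efficiency choice. It is worth only about 2 points at r = 0.7 without clustering. The list in section 4.1 already includes methods that could carry a good primary analysis. All of this stands, but it does not supply the missing designation.

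Four stronger readings are tempting, and the documents do not support them.

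- *The trial has only about 65% power.* That needs a low r and 0.75 on the T1 SD. Section 4.1 says "This study reported an effect size of 0.78 in increasing self-efficacy in labour", which is compatible with a change effect. On that reading the planned 80% is met, before clustering.
- *Adjustment wins at every r and costs nothing.* The factor 2/(1+r) is a large-sample result with equal SDs. Women register for courses and whole courses are randomised, so courses may already differ at T0, and then the gain shrinks or reverses. Section 3.3.1 describes women being randomised and then assigned to a class, which does not settle the matter.
- *The plan ignores the baseline or breaks intention to treat.* A pre-post design uses T0 as a repeated outcome. What is unstated is its role as a covariate. The listed mixed models could retain women without T1.
- *Seven to fourteen women will be lost from the primary test.* Section 3.4 expects non-completion of the class to be rare, and section 4.2 links loss to the course of the birth, which comes after T1. Much of the loss may therefore fall later.

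**Conclusion.** The point holds in a limited form. Section 4.1 does not determine the primary analysis: model, tested term, time point and role of baseline CBSEI are all open. If the two-time group-by-time test decides, it is a valid change-score comparison that is usually less precise than T1 adjusted for T0.

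Without clustering and with 0.75 on the T1 SD, the gain at 29 per arm is about 17, 9 and 2 percentage points at r = 0.3, 0.5 and 0.7. On the change-score SD it is about 13, 9 and 5 points above a planned 80%. These figures assume equal SDs, and r is not in the documents. Course-level randomisation lowers power for both tests. The gain persists if course effects arise only at T1, but with a stable course effect at both times it is about nil at an ICC of 0.10 and negative at 0.15.

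The missing analysis assignment for once-measured outcomes and the undocumented basis of the 29 per arm are gaps in detail. They do not carry the finding. The change is worth making, but its absence does not invalidate the trial.

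**What to change.** In section 4.1, replace repeated-measures ANOVA for the primary outcome with one named primary analysis of CBSEI at T1 adjusted for T0, in one of two forms:

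- a mixed model of T0 and T1 with arm means constrained equal at T0, which keeps every randomised woman with at least one score under missing at random; or
- T1 regressed on T0, with multiple imputation committed to in section 4.2.

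In either form, allow a course effect at both T0 and T1. In the regression form, also adjust for the course-mean T0 score or show that as a sensitivity analysis. Use small-sample degrees of freedom and report the T1 arm difference with its 95% CI. Make the other listed methods named sensitivity analyses. Do not apply repeated-measures ANOVA to once-measured outcomes (Apgar, cord pH, labour duration). Reconcile the CBSEI time points in sections 2.2, 2.3 and 3.3, and state r and the SD behind 0.75.

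The cost is SAP wording, R code, one degree of freedom, and a possible small loss of precision if courses already differ strongly at T0. No new data or participants are needed.

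### Sections 4.1 and 4.2 attach two unreconciled attrition rates (20% and about 10%) to one sample size calculation; only 20% gives 35 per arm, and as a minor point it is applied by multiplication, which leaves 28 rather than 29

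*Combined protocol and SAP*

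**What the plan says.** Section 4.1 bases the sample size on childbirth self-efficacy. It cites a reference trial with an effect size of 0.78 and attrition of about 30.7%, and continues: "we therefore assume an overall moderate effect size of 0.75". With 80% power and a 5% significance level, which the section states to be two-sided, it concludes: "a sample size of 29 per arm is needed for a two-arm repeated measures design (GPower, version 3.1"). It then adds the allowance for loss: "Assuming an attrition rate of 20%, the final sample size will be 35 in each arm and 70 participants in total".

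Section 4.2, on missing data and drop-outs, states: "The dropout rate is estimated at about 10 % and was taken into account accordingly in the sample size calculation". Section 3.4 mentions the allowance but gives no rate: "The loss of follow-up was considered in the sample calculation".

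The instrument table in section 3.3 places the self-efficacy inventory at baseline (T0) and in the questionnaire at around 36 weeks (T1), whose content is given as "Data about the antenatal education class, German versions of the Childbirth-Self-Efficacy Inventory". The table does not list it at the postnatal questionnaire (T3). No section gives attrition by time point.

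**The concern.** Section 4.2 does more than forecast a 10% loss; it says that this rate entered the calculation. Section 4.1 shows the calculation, and the rate there is 20%. A reader cannot tell what loss the trial is planned to withstand. The choice also decides whether the design meets its own requirement: from 35 per arm, a 10% loss leaves more than the stated 29 and a 20% loss leaves fewer.

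The second question is how the allowance was made. To retain n after losing a fraction a, the enrolled number must be n/(1 − a). Multiplying n by (1 + a) gives a smaller number, and the figure of 35 looks as if it came from multiplication.

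**Working it through.** **Inputs.** From section 4.1: effect size 0.75 (read here as Cohen's d, since the metric is not named), two-sided 5% level, 80% power, 29 per arm, 20% attrition, 35 per arm and 70 in total. From section 4.2: about 10% dropout.

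**Step 1: reproduce 29.** A two-sample t-test with d = 0.75, two-sided 0.05 and 80% power needs 28.90 per arm, so 29. This matches. A group-by-time interaction with two measurements, f = 0.75/4 = 0.1875 and an assumed correlation of 0.5 gives the same power as the t-test, and so the same 29.

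**Step 2: which rate gives 35?**

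| Rate | n × (1 + a) | n / (1 − a) |
|---|---|---|
| 20% | 29 × 1.2 = 34.8, so **35** | 29/0.8 = 36.25, so 37 |
| 10% | 29 × 1.1 = 31.9, so 32 | 29/0.9 = 32.2, so 33 |

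On the total, 58 × 1.2 = 69.6, so 70, which also matches. Of the four combinations, only 20% by multiplication gives 35 and 70.

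**Step 3: what remains from 35 per arm?**

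- 20% loss: 35 × 0.8 = 28, one below 29.
- 10% loss: 35 × 0.9 = 31.5, taken as 31, above 29.
- Largest loss that still keeps 29: 1 − 29/35 = 17.1%.

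**Step 4: power for d = 0.75** (two-sided two-sample t-test at 0.05, before any allowance for course-level clustering).

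| Per arm | Power |
|---|---|
| 28 | 78.7% |
| 29 | 80.1% |
| 31 | 82.8% |

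The shortfall costs 80.1 − 78.7 = 1.4 points. With 28 per arm, 80% power is reached at d = 0.76.

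**Step 5: sensitivity to the model.** Section 4.1 names a repeated measures design but gives no correlation. For the two-measurement interaction with f = 0.1875, over an assumed range of correlations:

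| Correlation (assumed) | 56 women | 62 women |
|---|---|---|
| 0.3 | 64% | 69% |
| 0.4 | 71% | 76% |
| 0.5 | 79% | 83% |
| 0.6 | 87% | 90% |

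The level of power moves a good deal with the correlation. The cost of having 56 women instead of 58 does not: it is 1.2 to 1.6 points throughout.

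**The case against.** The strongest reply is that the two sections may mean different things. Section 4.1 speaks of attrition and section 4.2 of dropout. Section 3.3.1 names study dropouts and loss to follow-up side by side, and section 4.2 goes on to say that some loss for medical reasons is unavoidable. On that reading 10% is one component of a 20% total. A reader might infer that the two statements flatly exclude each other; the documents do not support going that far, because this reading is possible. But no section states it or says what the other component would be, so the text still needs reconciling. The repair must leave room for this answer and not simply overwrite one figure with the other.

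A second reply is that the 28-against-29 shortfall is trivial beside the uncertainty in the effect size and the correlation. That is fair as to weight, and it is why the point is secondary. It remains correct as arithmetic, because it uses only the plan's own 29, 20% and 35.

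A third reply is that 28 need not be the number available for self-efficacy. This stands. The inventory is listed only at T0 and T1, section 3.4 expects few women not to complete the class, and an intention-to-treat analysis with mixed models and possible multiple imputation is planned. If loss by T1 is below the whole-study rate, more than 28 per arm remain at T1.

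A reader might also infer that the final report must compare observed attrition with a planned rate. The documents do not require this. Section 4.1 asks only that deviations from the statistical plan be described and justified, and section 3.4 plans to compare the characteristics of dropouts and completers.

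**Conclusion.** The point holds. One calculation carries two loss rates, 20% in section 4.1 and about 10% in section 4.2, with nothing to reconcile or distinguish them, and only the 20% reproduces 35 per arm and 70 in total. This should be corrected, because whether the stated 29 per arm is delivered depends on which rate is meant.

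The use of multiplication is a minor, subordinate error. At 20% total loss it leaves 28 per arm, one short, at a cost of about 1.4 points of power. It does no harm if total loss is at most 17.1%, and so none at 10%. It does not show that the trial is materially underpowered.

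The contradiction and the 28-against-29 comparison rest on the plan's own figures alone. The power figures assume that 0.75 is Cohen's d and use a t-test that reproduces the stated 29; they ignore course-level clustering and would change under another model or correlation.

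**What to change.** Keep enrolment at 70 and make three text changes.

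1. State one total attrition rate for the self-efficacy analysis in both 4.1 and 4.2. If 10% is meant as one component of a 20% total, say so and name the other component.
2. Restate in 4.1 what 70 women deliver. At 20%: 28 per arm complete, with about 79% power for d = 0.75. At 10%: 31 per arm, with about 83%. Attach the condition: two-sided two-sample t-test at 0.05, before course-level clustering. If the original G*Power calculation used another model or correlation, recompute the power and state those settings.
3. Note that more women may remain at T1 if loss by then is below the whole-study rate.

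The cost is one or two sentences in 4.1 and one figure or clause in 4.2. If 20% is the total, the stated power becomes slightly less favourable, about 79% in place of 80%.
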